6.3.1.3. Prevalence of adverse events of interest by week

The number and percentage of participants who are experiencing a TEAE of interest (either onset or ongoing) each week (up to and including the follow-up visit, with week as appropriate based on the End of Treatment definition) will be tabulated by treatment group and week. A separate table representing the number and percentage by severity (mild, moderate or severe) will also be produced. These tables will be produced separately for each TEAE of interest.

To calculate the percentage each week, the total number of participants who experience the TEAE of interest at any time during the respective week will be the numerator and the total number of participants who had not discontinued from IP and/or the study prior to that

PFIZER CONFIDENTIAL DMB02-GSOP-RF02 8.0 Statistical Analysis Plan Template TMF Doc ID: 98.03 Page 36 of 61 respective week will be the denominator (note if a participant did discontinue from IP and/or the study during that respective week they would be included in the denominator).

A figure of the overall percentage (i.e. not by severity) per week will be produced, with week on the x-axis and a separate line for each treatment group. A separate figure of the percentage per week will also be produced, with week on the x-axis and a separate line for each severity, paged by treatment group. These figures will be produced separately for each TEAE of interest.

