7. DISCONTINUATION OF STUDY INTERVENTION AND PARTICIPANT DISCONTINUATION/WITHDRAWAL

7.1. Discontinuation of Study Intervention

It may be necessary for a participant to permanently discontinue study intervention. Reasons for permanent discontinuation of study intervention include the following:

- Criteria for a potential Hy's law case are met (see Appendix 6);
- Intent to become pregnant or pregnancy confirmed by β-hCG testing;
- Safety or tolerability concern arises, in particular if not responsive to symptomatic management, dosing with double-blind study intervention may be stopped in an individual participant at the discretion of the investigator;
- Based on mental health assessment as outlined in Section 8.2.6, should be discontinued from dosing at the discretion of the investigator.

If the criteria for permanent discontinuation are met, the site should notify the sponsor Medical Monitor or sponsor Clinician.

Note that discontinuation of study intervention does not represent withdrawal from the study. If study intervention is definitively discontinued, the participant will remain in the study to be evaluated for obesity, and will be expected to continue with all study visits and assessments as outlined in the SoA for the applicable cohort (see SoA for Cohorts 1 and 2, and SoA for Cohort 3), with the exception of dosing activities and assessment of PK. See the SoA for the applicable cohort (see SoA for Cohorts 1 and 2, and SoA for Cohort 3) for data to be collected at the time of discontinuation of study intervention and follow-up for any further evaluations that need to be completed.

In the event of discontinuation of study intervention, it must be documented on the appropriate CRF/in the medical records whether the participant is discontinuing further receipt of study intervention or also from study procedures, posttreatment study follow-up, and/or future collection of additional information.

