3.2.2. Safety Endpoint(s)

3.2.2.1. Adverse Event

If an adverse event has a start time of 00:00 and a start date that is equal to the date of first administration of IP, the adverse event start time will be imputed with the time of the first dose of administration of IP.

If an adverse event has an end time of 00:00 then the end time will be imputed as 23:59.

An adverse event is considered treatment emergent (TEAE) relative to a given treatment if the event starts during the effective duration of treatment (i.e. starting on or after the first dose but before the last dose plus lag time).

The effective duration of treatment is determined by the lag time. Any event occurring within the lag time, whether this occurs during a break in treatment or at the end of treatment, is attributed to the corresponding treatment period. The lag time is defined by the Pfizer Standard of 365 days post last dose of IP.

Adverse events occurring during the placebo run-in period (i.e. starting from Day -14, inclusive, up to and before the first dose of active treatment on Day 1) will be considered non-treatment emergent.

A 3-tier approach will be used to summarize TEAEs. Under this approach, TEAEs are classified into 1 of 3 tiers. Different analyses will be performed for different tiers (see Section 6.3.1.

Tier 1 events: These are prespecified events of clinical importance and are maintained in a list in the product's Safety Review Plan.

Tier 2 events: These are events that are not tier 1 but are "common." A Medical Dictionary for Regulatory Activities (MedDRA) preferred term (PT) is defined as a Tier 2 event if there are at least 5% of participants reporting the event in any of the standard titration or placebo groups or at least 2 participants reporting the event in any of the slow titration groups.

Tier 3 events: These are events that are neither Tier 1 nor Tier 2 events.

PFIZER CONFIDENTIAL DMB02-GSOP-RF02 8.0 *Statistical Analysis Plan Template* TMF Doc ID: 98.03 Page 17 of 61

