3.2.2.1.1. Adverse events of interest

The TEAEs of interest for additional reporting are: nausea, vomiting and diarrhoea (as defined based on preferred term). Based on emerging blinded data reviews, other AEs of interest may be added to this list, which would be documented with a SAP amendment or documented in the changes to planned analysis section in the CSR.

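### SAP 6.3.1.3 lets off-drug participants into the numerator of weekly prevalence but not the denominator, so the percentage for nausea, vomiting and diarrhoea can only err upward

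*SAP*

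**What the plan says.** SAP 3.2.2.1.1 names the events: "The TEAEs of interest for additional reporting are: nausea, vomiting and diarrhoea". SAP 6.3.1.3 then tabulates, by treatment group and week up to the follow-up visit, the number and percentage of "participants who are experiencing a TEAE of interest (either onset or ongoing) each week". A second table splits this by severity, and figures accompany both.

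The percentage is defined in one sentence. Above the line, "the total number of participants who experience the TEAE of interest at any time during the respective week will be the numerator". Below the line is "the total number of participants who had not discontinued from IP and/or the study prior to that" week. A note covers people who stop within the week: "note if a participant did discontinue from IP and/or the study during that respective week they would be included in the denominator". Nothing restricts the numerator to the people in the denominator.

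Two other provisions decide who can appear in the numerator. On treatment emergence, SAP 3.2.2.1 says: "The lag time is defined by the Pfizer Standard of 365 days post last dose of IP". On follow-up, Protocol 7.1 says: "If study intervention is definitively discontinued, the participant will remain in the study to be evaluated for obesity". Such participants keep all visits and assessments apart from dosing activities and PK. Protocol 8.3.1 collects adverse events for at least 28 days after the last dose.

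**The concern.** A participant who stops IP because of nausea in Week 6 and is still nauseated in Week 7 is counted above the line in Week 7 but removed below it. The same holds for a new event in someone already off drug.

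The SAP's version history (Table 1) shows how this may have come about. Version 2 added IP discontinuation to the denominator exclusion and records no matching change to the numerator. The neighbouring displays do not mix populations in this way. In 6.3.1.2, neither denominator removes people merely for stopping IP. In 6.3.1.4, follow-up is censored at IP or study discontinuation, which removes off-drug events and off-drug time together.

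At stake is the reading of tolerability over time by titration scheme, which Protocol 4.2 gives as a reason for adding Cohorts 2 and 3. The same section bars downward titration and says that participants who do not tolerate dosing may have to stop. IP stopping may therefore follow the very events being displayed, and need not be equal across arms.

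**Working it through.** The documents state no prevalence figure, so there is none to reproduce. The direction and form of the error follow from algebra.

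**Notation, for one arm and one week**
- A = on-drug participants with the event; B = participants off drug but still in study with the event.
- N_on and N_off = sizes of those two groups; d = N_off/(N_on + N_off); p_off = B/N_off.
- People who have left the study are taken to be absent from both parts.

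**Three percentages**
- SAP as written: (A + B)/N_on
- Consistent on-drug: A/N_on
- Consistent in-study: (A + B)/(N_on + N_off)

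**Comparisons**
1. SAP ÷ in-study = (N_on + N_off)/N_on = 1/(1 − d). Event rates cancel.
2. SAP − on-drug = B/N_on = p_off × d/(1 − d). This is never negative, and is zero only when no off-drug participant has the event (or nobody is off drug).

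The values of d and p_off below are assumptions, since the documents give neither:

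| d | SAP ÷ in-study | Excess over on-drug (points), p_off = 0 | p_off = 2% | p_off = 5% | p_off = 10% |
|---|---|---|---|---|---|
| 10% | 1.11 | 0 | 0.2 | 0.6 | 1.1 |
| 25% | 1.33 | 0 | 0.7 | 1.7 | 3.3 |
| 40% | 1.67 | 0 | 1.3 | 3.3 | 6.7 |
| 50% | 2.00 | 0 | 2.0 | 5.0 | 10.0 |

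**Worked example.** Take one Cohort 1 arm of 60 (Protocol 9.2), all still in study. Suppose 15 are off drug (d = 15/60 = 25%), with 5 on-drug and 2 off-drug participants nauseated that week; these counts are assumed.
- SAP: 7/45 = 15.6%
- On-drug: 5/45 = 11.1%
- In-study: 7/60 = 11.7%

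Protocol 9.2 plans for 25% drop-out, but does not split it between stopping IP and leaving the study. It is therefore not an estimate of d.

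**Differences between arms.** Two arms that each have 10% prevalence both on and off drug would print as 10%/(1 − 0.10) = 11.1% at d = 10%, and 10%/(1 − 0.50) = 20.0% at d = 50%. The ordering by d is not guaranteed against the on-drug percentage: d = 40% with p_off = 2% gives an excess of 1.3 points, while d = 25% with p_off = 5% gives 1.7.

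**The case against.** The best reply concerns size. Protocol 2.2.2.1 reports that adverse events in the earlier Phase 2 studies mostly went away once dosing stopped. If that holds here, B is small, the excess over the on-drug percentage is near zero, and what remains sits in the weeks just after stopping. This stands. It limits the size and leaves the definition mismatched. Even with B = 0, the figure equals the on-drug percentage and is still 1/(1 − d) times the in-study one.

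It can also be said that a programmer would match the two parts anyway. The SAP specifies the calculation, though, and a faithful program or independent check would reproduce it as written.

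The 365-day window carries less weight than it seems to, because the display ends at the follow-up visit. Only the part of the window up to that visit matters.

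Three stronger readings are tempting and are not supported:
- A reader might infer that prevalence is overstated by a fixed large amount, such as a third. That figure is exact only against the in-study percentage at d = 25%. Against the on-drug percentage it needs an off-drug event rate that the documents do not supply.
- A reader might infer that the overstatement is always largest where IP stopping is greatest. This is exact for the ratio to the in-study percentage. Against the on-drug percentage, it also needs similar off-drug event rates across arms.
- A reader might treat this as the principal tolerability display. SAP 6.3.1, 6.3.1.1, 6.3.1.2 and 6.3.1.4 to 6.3.1.6 give several others. SAP 6.3 says its figures may be left out of the CSR, and 6.3.1 calls safety analysis generally exploratory.

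**Conclusion.** The rule is wrong as written. Followed literally, it yields a percentage whose numerator can include people outside its denominator, and the error is never downward. Relative to an in-study percentage, the inflation is exactly 1/(1 − d): ×1.11 at 10% off drug and ×1.33 at 25%. Relative to an on-drug percentage, the excess is B/N_on, which runs from zero upward and cannot be sized from the documents.

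The conclusion rests on three things: IP discontinuers staying under observation, their events staying treatment-emergent, and the numerator sentence being applied as it reads. The bias can differ between arms when IP stopping differs, so it can distort comparisons between titration schemes and with placebo in this display. The participant counts printed beside the percentages are unaffected, as are the efficacy analyses, and no stated test or decision rule uses this percentage.

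**What to change.** Use one population in both parts. To keep the denominator that version 2 introduced, define the numerator as participants in that week's denominator (not discontinued from IP or the study before the week) who experience the event during the week. Apply this to the overall and by-severity tables and to the figures. Same-week stoppers then remain in both parts for that week.

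Also state that completing treatment is not discontinuation from IP. The display runs to the follow-up visit, when completers are off drug too; without that sentence, the denominator for those weeks is undefined and could fall close to zero.

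The cost is a clause and a sentence in the SAP and one filter in the program. Events in off-drug participants leave this display but remain in the overall TEAE tables. If the sponsor wants those events shown week by week, in-study over in-study is equally coherent, but it would mean reversing the version 2 denominator change.

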6.3.1.4. Time to First Occurrence/Recurrence of AEs of Interest

Exploratory summaries on the time to the first occurrence of AEs of interest will be produced in Cumulative Incidence Plots as described in Section 5.2.7. Participants who discontinue from the study or discontinue from IP prior to the start of the AE event of interest will be censored at the discontinuation/initiation date.

A separate plot for each AE of interest will be produced separately.

The above will also be produced separately for the time to the first recurrence of the AEs of interest.

6.3.1.5. Time to discontinuation from IP due to Gastrointestinal Disorders AEs

Exploratory summaries on the time to discontinuation from IP (regardless of study discontinuation or continuation) due to Gastrointestinal Disorders AEs (defined as based on System Organ Class) will be produced with a Cumulative Incidence Plot as described in Section 5.2.7. Participants who discontinue will be censored at the associated discontinuation date.

6.3.1.6. Subset Reporting Interval

The subset adverse events, described in Section 3.2.2.1.2, will be summarised as above (excluding the 3-tier reporting system) where standard tables and incidence tables will be produced for both 'All causality' and 'Treatment related'.

6.3.1.7. Hypoglycemic Adverse Events

The hypoglycemic AEs will be listed in a separate table and summarized categorically by treatment group and overall as per Section 5.2.1.

6.3.2. Laboratory Data

Laboratory data from will be listed and summarized by treatment group and overall, in accordance with the sponsor reporting standards.

6.3.2.1. Focused Laboratory Summaries on Endpoints of Interest

Absolute values, changes from baseline and percent changes from baseline in calcitonin, amylase, lipase, TSH, free T4, lipid profile, liver function tests and eGFR (as outlined in Section 3.2.2.3) will be summarized by treatment group and time point as per Section 5.2.1 (unplanned readings will not be included in these summaries). Follow-up data will be including in the summaries with data from all participants in the safety analysis set. Tables will be paged by parameter.

PFIZER CONFIDENTIAL DMB02-GSOP-RF02 8.0 *Statistical Analysis Plan Template* TMF Doc ID: 98.03 Page 37 of 61 The following box and whisker plots for each parameter will be produced:

- Absolute values over time by treatment group
- Change from baseline over time by treatment group
- Percentage change from baseline over time by treatment group.

Spaghetti plots for individual data versus time, by treatment, will be produced for ALT, ALP, AST and total bilirubin:

Plots of absolute values of ALT and AST versus change from baseline in weight by treatment will also be produced.

MMRM models (as described in Section 5.2.3) will be applied to the change from baseline at Weeks 4, 8, 12, 16, 22 and 26 (as applicable) for Cohorts 1 & 2 and at Weeks 4, 8, 12, 16, 20, 24, 28 and 32 for Cohort 3 separately and for each parameter separately using the safety analysis set (as defined in Section 4). For ALT, AST, alkaline phosphatase and GGT, the MMRM models will instead be applied to the change from baseline on the natural log scale and the MMRM results will be back-transformed for reporting, similar to the primary endpoint as described in Section 6.1.1.1.

From each model, the LSMeans together with 90% confidence intervals, standard errors and p-values will be obtained for each treatment group at each time point. Differences in LSMeans between each treatment group of danuglipron relative to placebo at each time point, together with 90% confidence intervals, standard errors and 2-sided p-values will also be obtained. A plot of the LSMean differences to Placebo (including 90% confidence intervals) over time, with a separate line for each treatment group of danuglipron will be produced separately for each parameter. Standard SAS outputs will be provided to support the main statistical summary tables but will not be included in the CSR.

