| Blood sampling for: | | | | | | | | | | | | | | | | |
| Hematology, Chemistry (including FPG and eGFR) | × | | × | × | × | × | × | × | × | X | × | × | X | × | | × |
| FSH (females only); C-peptide | X | | | | | | | | | | | | | | | |
| Pregnancy test (all females) ^o | X | X | X | X | X | Х | X | X | X | X | X | X | X | X | | X |
| HbA1c | X | | X | | | | | | | Х | | | X | | | X |
| Lipids, TSH, free T4, calcitonin, amylase, lipase, TBA, PT/INR/aPTT, FPI | X | | x | | х | | × | | x | x | | х | х | x | | × |
| PF-06882961 PK (pre-dose unless noted) | | | X^{m} | | X | | X^{m} | X | | X^{m} | | | \mathbf{x}^{m} | | | X |
| Banked biospecimen: Prep B1 & B2 | | | X | | | | | | | X | | | X | | | X |
| Banked biospecimen: Prep D1 (only Day 1) ⁿ | | | X | | | | | | | | | | | | | |
| Urine Sampling for: | | | | | | | | | | | | | | | | |
| Urine drug screen | X | | | | | | | | | | | | | | | |
| Urinalysis (and microscopy, reflexive) | X | | X | | X | | X | | X | Х | | Х | Х | Х | | X |
| On-site urine pregnancy test (all females)° | | × | X | × | × | × | × | × | × | X | X | X | X | × | | X |

PFIZER CONFIDENTIAL CT02-GSOP Clinical Protocol Template Phase 1 2 3 4 (05 December 2019) Page 24

- Final Protocol Amendment 2, 16 September 2022
- a. **End of Treatment:** Defined as Week 26.
- Study part and Follow-up: In Part A (Weeks 1-16) participants will be randomized and dosed with double-blinded study intervention on Day 1 and dosing will continue through 16 weeks. In Part B (Weeks 17-26) participants in Part A will continue dosing, according to randomization from Part A.
- Early termination/discontinuation: This visit applies only to participants who are enrolled/randomized and then are prematurely withdrawn from the study, ie, permanently discontinued both from the study intervention and from the study. Note: discontinuation of study intervention does not represent withdrawal from the study. If only study intervention is discontinued, the participant will remain in the study and continue with all visits and assessments (except for dosing activities and assessment of PK). See ပ
- Days relative to Dosing on Day 1: Dosing occurs on Day 1 and timing of subsequent visits is determined by adding the number of days noted to Day 1. For example, V4 is Day 1+14 days (± 3 days), V5 is Day 1+28 days (± 3 days), etc. ġ.
- e. Follow-up V15: Visit may be a phone call. f. Site based PROs: Completed at the site on

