| Potential Risk of Clinical Significance | Summary of Data/Rationale for Risk | Mitigation Strategy |
|--|---|---|
| Impairment in renal function | The potential risks are based on product labeling for peptidic marketed GLP-1R agonists, and predominantly occur in patients with significant nausea, vomiting, and dehydration. Data from the completed clinical studies with PF-06882961 do not suggest an increased risk to renal function. | Per exclusion criteria, potential participants with significant renal impairment (<60 mL/min/1.73 m²) are not eligible for study entry. Renal function is monitored at each study visit by the central lab assessments of serum BUN, creatinine and eGFR. |
| Gastrointestinal adverse reactions | The potential risks are based on product labeling for peptidic marketed GLP-1R agonists (ie, semaglutide, liraglutide, exenatide and dulaglutide). Gastrointestinal AEs, the majority of which were mild in severity, have been observed in the clinical program with PF-06882961. In nonclinical studies with PF-06882961, gastrointestinal adverse effects have been seen in rats and monkeys. | Participants are monitored during the clinical study visits, via body weight, vital signs and laboratory assessments, to prevent potential sequelae of any severe gastrointestinal reactions, eg. dehydration. |
| Diabetic retinopathy complications | The potential risk is based on the product labeling for the peptidic GLP-1R agonists semaglutide and dulaglutide where patients with T2DM and diabetic retinopathy who are taking these agents should be monitored for progression of diabetic retinopathy, as rapid improvement in glucose control has been associated with a temporary worsening of diabetic retinopathy. This risk has not been listed in the prescribing information for other marketed GLP-1R agonists. There are no nonclinical or clinical data involving PF-06882961 to suggest an increased risk of diabetic retinopathy complications. | Potential participants with diabetes mellitus are excluded from this clinical study. |

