3.2.2.3.1. Change from Baseline Summaries

Focused change from baseline summaries (including both absolute changes from baseline and percent change from baseline, calculated separately) of the following safety laboratory endpoints will be assessed:

- Change from baseline in calcitonin to all post-dose time points as per the SOA
- Change from baseline in amylase to all post-dose time points as per the SOA
- Change from baseline in lipase to all post-dose time points as per the SOA
- Change from baseline in thyroid stimulating hormone (TSH) to all post-dose time points as per the SOA
- Change from baseline in free thyroxine (free T4) to all post-dose time points as per the SOA
- Change from baseline in lipid profile (total cholesterol, direct LDL cholesterol, HDL cholesterol and triglycerides) to all post-dose time points as per the SOA
- Change from baseline in liver function tests (alanine transaminase [ALT], aspartate aminotransferase [AST], alkaline phosphatase, total bilirubin, bile acids and gamma-glutamyl tranferase [GGT]) to all post-dose time points as per the SOA
- Change from baseline in estimated glomerular filtration rate (eGFR) to all post-dose time points as per the SOA

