6.4.7. CFB in lipid parameters over time

In all cases a dataset similar to Estimand Set 1 as specified in Section 4 will be utilised.

Absolute and change from baseline in lipid parameters will be summarised descriptively and analyzed as described in Section 6.3.2.1 at Weeks 2, 4, 6, 8, 10, 12, 16, 18, 22 and 26 for Cohorts 1 & 2 and at Weeks 4, 8, 12, 16, 20, 24, 28 and 32 for Cohort 3 separately.

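### For six chemistry parameters in Cohorts 1 & 2, the SAP 6.3.2.1 MMRM covers only six of the ten on-treatment visits at which they are measured, leaving out Weeks 2, 6, 10 and 18

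*SAP*

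**What the plan says.** In SAP 6.3.2.1, results for "calcitonin, amylase, lipase, TSH, free T4, lipid profile, liver function tests and eGFR (as outlined in Section 3.2.2.3) will be summarized by treatment group and" visit. The same section then specifies MMRMs for each of these parameters, which "will be applied to the change from baseline at Weeks 4, 8, 12, 16, 22 and 26 (as applicable) for Cohorts 1 & 2". The Cohort 3 list is Weeks 4, 8, 12, 16, 20, 24, 28 and 32.

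SAP 3.2.2.3.1 defines the endpoints more widely. For kidney function it reads "Change from baseline in estimated glomerular filtration rate (eGFR) to all post-dose time points as per the SOA". The liver-test entry (ALT, AST, alkaline phosphatase and others) ends "total bilirubin, bile acids and gamma-glutamyl tranferase [GGT]) to all post-dose time points as per the SOA".

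The SoA for Cohorts 1 and 2 (Protocol 1.3.1) has two relevant blood-sampling rows. The row beginning "Hematology, Chemistry (including FPG and eGFR" is marked at every on-treatment visit. The row "Lipids, TSH, free T4, calcitonin, amylase, lipase, TBA, PT/INR/aPTT, FPI" is marked on treatment only at Weeks 4, 8, 12, 16, 22 and 26. Protocol Appendix 2, Table 6 places ALT, AST, total bilirubin, GGT, alkaline phosphatase and eGFR under Chemistry, and total bile acids under Other.

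SAP 6.4.7 states: "Absolute and change from baseline in lipid parameters will be summarised descriptively and analyzed as described in Section 6.3.2.1 at Weeks 2, 4". Its Cohorts 1 & 2 list continues through 6, 8, 10, 12, 16, 18, 22 and 26. SAP 3.4 gives the lipid endpoint at Weeks 4, 8, 12, 16, 22 and 26.

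**The concern.** A single visit list is applied to parameters that follow two different sampling schedules. It fits one schedule and is too short for the other. The qualifier in brackets in SAP 6.3.2.1 does not repair this: it can remove a listed week for a parameter not drawn then, but it cannot add an unlisted one.

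The omitted visits fall while doses are being raised. The protocol's risk table connects renal impairment with marked nausea, vomiting and dehydration, and as mitigation says: "Renal function is monitored at each study visit by the central lab assessments of serum BUN, creatinine and eGFR". The MMRM is the planned source of covariate-adjusted differences from placebo over time. For eGFR and the five liver tests it would give no estimate before Week 4 and would have gaps after that. A participant with a Week 2 chemistry value but no value at any listed visit adds no outcome to these models.

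**Working it through.** No sample-size or error-rate figure is involved, so the check is a comparison of visit lists followed by a count.

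**Step 1. On-treatment visits in Cohorts 1 & 2**

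| Source | Weeks | Count |
|---|---|---|
| SoA, chemistry row | 2, 4, 6, 8, 10, 12, 16, 18, 22, 26 | 10 |
| SoA, lipids/TSH/bile acids row | 4, 8, 12, 16, 22, 26 | 6 |
| MMRM list, SAP 6.3.2.1 | 4, 8, 12, 16, 22, 26 | 6 |
| Lipid list, SAP 6.4.7 | 2, 4, 6, 8, 10, 12, 16, 18, 22, 26 | 10 |

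The MMRM list equals the second SoA row exactly. Chemistry weeks minus MMRM weeks leaves 2, 6, 10 and 18, so 4 of 10 (40%) are omitted. The SAP 6.4.7 lipid list has the opposite fault: the same four weeks are named although no lipids are scheduled then.

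**Step 2. Parameters affected.** Counting single analytes, the focused set has 16: calcitonin, amylase, lipase, TSH and free T4 (5), four lipids, six liver tests including bile acids, and eGFR (5 + 4 + 6 + 1 = 16). The six-visit list is right for 10 of them (5 + 4 + bile acids) and too short for 6: ALT, AST, alkaline phosphatase, total bilirubin, GGT and eGFR.

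**Step 3. Share of titration visits omitted.** SAP 2.3 gives the longest titration as 10 weeks in the 1-week arms and 20 weeks in the 2-week arms.

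- 1-week arms, visits up to Week 10: 2, 4, 6, 8, 10. Omitted: 2, 6, 10, so 3 of 5. If Week 10 is counted as the end of titration, the visits are 2, 4, 6, 8 and the omitted ones 2 and 6, so 2 of 4.
- 2-week arms, visits up to Week 20: 2, 4, 6, 8, 10, 12, 16, 18. Omitted: 2, 6, 10, 18, so 4 of 8.
- Lower target doses have shorter schedules, which are redacted. Taking every cut-off from 2 to 20 weeks, the omitted share runs from 3 of 7 (43%, cut-off Week 16 or 17) to 1 of 1 (cut-off Week 2 or 3).

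**Step 4. Is a six-visit policy for safety models evident elsewhere?** FPG shares the chemistry row of the SoA with eGFR, and SAP 6.2.6 models it at all ten weeks. The ECG models (SAP 6.3.4) use the same ten weeks, and the vital-sign models (SAP 6.3.3) include Weeks 2, 6, 10 and 18. No reason is given for treating ALT or eGFR differently from FPG drawn at the same visit.

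**Step 5. Cohort 3.** Its MMRM list matches the in-clinic chemistry visits in its own SoA, so it is not affected.

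**The case against.** The best defence is that the omission touches a supplementary layer only. Protocol 9.4.5 commits to descriptive safety summaries; the laboratory MMRM goes beyond that. SAP 5.1 plans no formal testing of safety endpoints, SAP 6.3.1 describes safety analysis as generally exploratory, and SAP 6.3 says its figures may not reach the CSR. SAP 3.2.2.3.1 can be read as governing the descriptive summaries alone, which SAP 6.3.2.1 delivers without a restricted visit list. The MMRM also leaves out the follow-up visit for every parameter, so it was never meant to cover all scheduled time points. This stands, and it weakens the conflict with SAP 3.2.2.3.1. It does not explain why FPG is modelled at ten visits and eGFR from the same SoA row at six.

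Four stronger readings are tempting, but the documents do not support them.

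- A reader might infer that the model skips most titration visits. That holds for the longest 1-week titration only if Week 10 is counted within it. In the longest 2-week titration it is exactly half.
- A reader might infer that early safety data go unreported. They do not. The descriptive tables and box plots include all these visits, there are individual-profile plots for ALT, AST, alkaline phosphatase and total bilirubin, and the flag/alert table uses all post-baseline values (SAP 3.2.2.3.2). That table has no eGFR line, but it has a creatinine rise from baseline.
- A reader might infer that all liver tests are affected. Bile acids are not drawn at the omitted weeks and are correctly on the six-visit list.
- A reader might infer that the lists in SAP 6.3.2.1 and 6.4.7 were swapped. This is conjecture: putting the ten-visit list into 6.3.2.1 for everything would be wrong for 10 of the 16 parameters, and one common grid applied to all is just as plausible.

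Two further limits apply. The protocol's renal risk row also says that completed studies do not suggest increased renal risk. And participants who only stop study drug stay in the study with all assessments (Protocol 7.1), so the number who contribute a Week 2 value and nothing later may be small; the documents do not allow an estimate.

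**Conclusion.** The mismatch is real and limited in scope. In Cohorts 1 & 2, four of ten scheduled on-treatment visits are missing from the modelled placebo-adjusted estimates, and their plots, for six of the 16 focused laboratory parameters. At least half of the visits in each of the two longest titrations are affected: 3 of 5 (or 2 of 4) in the 1-week arms and 4 of 8 in the 2-week arms. Separately, SAP 6.4.7 cannot be carried out as written for lipids at Weeks 2, 6, 10 and 18.

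Efficacy results, descriptive safety outputs, abnormality counts and Cohort 3 are untouched. The conclusion rests on the SoA rows as printed, on Table 6 for which analytes belong to the chemistry panel, and on the maximum titration lengths in SAP 2.3. It is worth correcting because the data exist and the correction is cheap, not because the trial's safety conclusions depend on it.

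**What to change.** In SAP 6.3.2.1, replace the single Cohorts 1 & 2 list with two:

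- ALT, AST, alkaline phosphatase, total bilirubin, GGT and eGFR: Weeks 2, 4, 6, 8, 10, 12, 16, 18, 22 and 26.
- Calcitonin, amylase, lipase, TSH, free T4, lipids and bile acids: Weeks 4, 8, 12, 16, 22 and 26, as now.

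In SAP 6.4.7, change the Cohorts 1 & 2 lipid weeks to 4, 8, 12, 16, 22 and 26, in line with SAP 3.4 and the SoA.

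The cost is SAP wording and a visit filter in six models. The unstructured covariance matrix grows from 6 × 7 / 2 = 21 to 10 × 11 / 2 = 55 parameters. A ten-visit model is already planned for body weight, FPG and ECG, and SAP 5.2.3 already provides for other covariance structures if the fit does not converge.
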